6.1 Participant population

All participants enrolled in CFAN were adults, and at least two first-degree relatives had AD. All participants received clinical assessment and genetic testing at baseline. Based on whether carrying a pathogenic mutation of the *PSEN1*, *PSEN2*, or *APP*, the cohort was further divided into two subgroups: autosomal dominant AD and unknown gene mutation FAD (un-FAD).

Subjects come from three sources:

1) FAD family in the memory clinic of Xuanwu Hospital.

2) FAD family recruited from CFAN subsites, where recruitment was according to the study protocol.

3) Online registration through the CFAN website (www.Chinacfan.org) and submission of basic demographic data and family information to CFAN. The CFAN administrator selects the family that meets inclusion criteria by reviewing the online registration materials, and recommends them to the CFAN subsite or Xuanwu Hospital memory clinic according to the geographical location.

6.2 Inclusion criteria

(1) Written informed consent obtained from the participant or a legal guardian prior to any study-related procedures;

(2) At least two first-degree relatives in a family have AD (clinically or by testing), and at least 3 out of 2 generations are patients;

(3) At least one family member with normal cognitive function (the age should be greater than the average age of onset of the family);

(4) Pedigrees carrying FAD pathogenic genes (*APP/PSEN1/PSEN2*);

(5) People in this family >18 years old can be recruited;

(6) Participant is cognitively normal or demented but not reaching bedridden level;

(7) Participants are able to provide two reliable informants who can provide clinical information;

(8) Dementia is diagnosed according to the criteria described by the Diagnostic and Statistical Manual of Mental Disorders, Fourth Edition, Text Revision (DSM-IV-R [31]);

(9) The diagnosis of AD is made using the National Institute of Neurologic and Communicative Disorders and Stroke and the Alzheimer's Disease and Related Disorders Association (NINCDS-ADRDA [32]) or National Institute on Aging and the Alzheimer's Association (NIA-AA) criteria [33];

(10) The diagnosis of MCI is made according to Petersen criteria [34] and the classification is according to the method of Lopez et al [35].

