2.1 Overview

CFAN is the world's second largest registry network started by [name] in 2005. The sponsor of this project is Xuanwu Hospital of Capital Medical University. CFAN is a multicenter observational longitudinal cohort study. The main research population for CFAN are autosomal

dominant inherited AD and unknown gene mutation AD family. All CFAN participants will be assessed longitudinally with comprehensive clinical, cognitive, genetic, imaging, and biomarker examinations, and all data will be collected using a unified standard, and stored into a central database. The purpose of the establishment of CFAN is to advance the research progress of FAD new mutations, pathogenic mechanisms and biomarkers in the Chinese population. At the same time, CFAN has great clinical significance. Through gene screening of the family, asymptomatic gene carriers can be found earlier, early diagnosis and intervention can be performed, and the prognosis can be improved. Long-term follow-up of asymptomatic gene carriers is convenient to further reveal the evolution of AD disease, and to find a breakthrough for early diagnosis and intervention in the population of asymptomatic gene carriers.

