2.4 Sample size

There will be a total of 40,000 subjects participating in this project. The total number of subjects to be included in this hospital is 5,000, and other sites include 400-600 persons per sites.

3. Research aims

This research will establish and continuously improve the FAD research network in conjunction with multi-center institutions nationwide. By collecting information on the family's demography, genetics, neuropsychology, neuroimaging, biomarkers and other information, we can understand the current FAD population in China, clarify the genetic characteristics, pathogenesis, disease characteristics and diagnosis and treatment status of AD in China; which will lay the foundation for ameliorating clinical diagnosis and treatment, establishing a Chinese FAD clinical database and an international cooperative research platform.

3.1 To set up a multi-center, nationwide FAD research network and database platform in China

The network and database include ADAD cohort of the known mutations of *PSEN1*, *PSEN2* and *APP* (mutation carriers and noncarriers; pre-symptomatic and symptomatic) and unknown mutations cohort.

3.2 To clarify the epidemiological characteristics of FAD in China.

Conduct a comprehensive FAD epidemiological survey in China to clarify the impact of different nationalities, regions, gender, age, living environment (rural/urban), education level, etc. on the

occurrence and development of the disease.

3.3 To clarify the genetic characteristics of FAD in China.

This project is to discover new FAD mutation sites, pathogenic genes, to protective genes, to explore the pathogenic and protective mechanism, to analyze the disease development laws of families with different sizes of FAD in China, and to clarify the frequency distribution of mutant genes in the Chinese FAD population.

3.4 To clarify the clinical characteristics and disease development laws of FAD in China.

The project will collect and regularly follow-up the samples (blood, urine and saliva etc.) and data (neuropsychology, imaging etc.) in the cohort. Emphasis is placed on the occurrence and development of asymptomatic mutant gene carriers from asymptomatic to symptomatic periods.

3.5 To discover and verify the early diagnosis biomarkers of AD.

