4.1 Cohorts

We recruit Pre-MCI, MCI and AD dementia patients and normal cognitive control people to establish horizontal and vertical research cohorts, including ADAD cohort and the unknown mutation carrier cohort. Establish a national FAD research network and electronic database platform to improve the clinical information database and biological sample database.

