6.4 Study discontinuation

The primary reasons for study discontinuation are:

(1) Protocol violation. The participant fails to meet inclusion criteria, or meets exclusion criteria.

(2) Participant is unwilling or unable to participate.

(3) Consent is withdrawn.

(4) The study is terminated by the project director or the CFAN administration center.

(5) Safety Risk. Any participant who develops safety risk at any time during the visit.

(6) Death.

(7) Others.

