7.3 Procedures for genetic studies

7.3.1 Gene testing

The goal of the genetic study of CFAN is the genetic information and useful biological materials (DNA, blood, cerebrospinal fluid, urine, saliva, etc.) provided by cognitive normal and dementia in the ADAD cohort and unknown gene mutation cohort. It is anticipated that collection of these data will facilitate clinical and basic science investigations of the pathogenesis of dementia.

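### Inclusion criterion 6.2(4) requires a known APP/PSEN1/PSEN2 mutation in the pedigree, which shuts out the unknown-mutation cohort that the rest of the protocol enrols

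*Protocol*

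**What the plan says.** Section 6.2 gives ten numbered inclusion criteria. Item (4) reads "Pedigrees carrying FAD pathogenic genes", followed by the three gene names in brackets. It is not offered as an alternative to another item and carries no cohort label.

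Five other sections describe a study that also takes in families without such a mutation:

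- **2.1** gives the main population as autosomal "dominant inherited AD and unknown gene mutation AD family".
- **Aim 3.1** sets up an ADAD cohort ("mutation carriers and noncarriers; pre-symptomatic and symptomatic) and unknown mutations cohort").
- **4.1** describes the cohorts as "including ADAD cohort and the unknown mutation carrier cohort".
- **6.1** has all participants genetically tested at baseline and, according to whether a pathogenic PSEN1, PSEN2 or APP mutation is carried, "the cohort was further divided into two subgroups: autosomal dominant AD and unknown gene mutation FAD (un-FAD").
- **7.3.1** again refers to "dementia in the ADAD cohort and unknown gene mutation cohort".

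The inclusion list is used operationally in three places. For online registrations, 6.1 states "The CFAN administrator selects the family that meets inclusion criteria". Section 6.4(1) treats as a protocol violation, and a reason for discontinuation, the case in which "The participant fails to meet inclusion criteria, or meets exclusion criteria". Section 9.3 has the inclusion and exclusion criteria confirmed before the database is generated.

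**The concern.** The eligibility list and the description of the population disagree about who may enter, and either way of resolving that in practice causes harm.

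- **If item (4) is applied**, the un-FAD cohort is empty. The proportion of FAD families with a known mutation, which is part of aim 3.3, cannot be estimated from a sample selected on having one. The families in which new pathogenic genes would be sought are absent. The split among the three genes, and among variants within them, would still be estimable.
- **If item (4) is not applied**, most pedigrees are violations under 6.4(1) and fail the check in 9.3.

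With 68 centres, a third possibility is that sites differ. The mix of mutation-positive and mutation-negative families would then depend partly on how each site read one line.

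**Working it through.** No sample-size or power figure is at issue. The check compares the texts and then uses simple arithmetic to show the scale.

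**Can the texts be read together?**

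1. *Could an unknown-mutation family still carry an APP/PSEN mutation?* No. Section 6.1 makes the division on whether a pathogenic mutation in those three genes is carried, so un-FAD is the group without one.
2. *Could un-FAD mean noncarrier relatives within ADAD families?* No. Aim 3.1 already places noncarriers inside the ADAD cohort.
3. *Could item (4) be checked at entry?* Not for a family that has never been tested. Section 6.5 lists the eligibility check as item (3) and genetic testing as item (5). That order suits a classification made after enrolment, not an entry condition.

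**Scale**

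Inputs, from the last paragraph of section 1: 13.12% of pedigrees with PSENs/APP missense mutations, 3.71% with synonymous or untranslated-region variants, and 83.17% with neither. Sum: 13.12 + 3.71 + 83.17 = 100.00%.

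Share failing item (4):

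- counting only pedigrees with no mutation: 83.17%
- also counting synonymous/untranslated-region variants as not pathogenic: 83.17 + 3.71 = 86.88%

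**Denominator.** Section 1 names 514 pedigrees, but no whole count out of 514 gives these percentages. The number 404, from the title of the mutation study cited as reference [30], gives all three:

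| Stated share | × 514 | Nearest counts on 514 | On 404 |
|---|---|---|---|
| 13.12% | 67.4 | 67 = 13.04%, 68 = 13.23% | 53 = 13.12% |
| 3.71% | 19.1 | 19 = 3.70% | 15 = 3.71% |
| 83.17% | 427.5 | 427 = 83.07%, 428 = 83.27% | 336 = 83.17% |

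53 + 15 + 336 = 404. On that base, 336/404 = 83.17% and (336 + 15)/404 = 351/404 = 86.88% fail. The conclusion needs only the shares, not the base.

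**Illustration only.** If pedigree shares carried over to individuals, 0.8317 × 40,000 = 33,268 and 0.8688 × 40,000 = 34,752 of the planned 40,000 subjects (section 2.4) would be barred. Family sizes differ, so these are not estimates.

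**The case against.** The strongest reply is that section 6.2 is not a uniform set of gates. It has no lead-in requiring every item. Items (8) to (10) are diagnostic definitions that a cognitively normal participant, admitted by item (6), cannot satisfy. In such a list, item (4) can be read as an ADAD item that lost its label. Five sections state the intended population consistently, and section 1 reports pedigrees without mutations as enrolled, so the criterion has evidently not operated as a gate. It is also not shown which protocol version governed those pedigrees. For online registrations, the material reviewed is demographic and family information, so genotype may not be considered at that step.

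Much of this is fair. Item (4) probably was meant for the ADAD cohort, and the harms are conditional on how it is used. Calling the pedigrees in section 1 actual violations would go too far. But the text does not contain the label, and 6.4(1) and 9.3 refer to the inclusion criteria without exempting any item.

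Three narrower objections also have weight. The 404 base is an inference from a reference title. The projection to 40,000 rests on an unsupported assumption. The faults in items (2) and (6) are separate and minor. None of these affects the conflict over item (4).

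**Conclusion.** The contradiction is real and should be corrected. As worded, item (4) excludes a cohort that the aims require, and no reading of sections 3.1 and 6.1 removes the conflict. Between 83.17% and 86.88% of pedigrees fail it, on the percentages in section 1. The range depends only on whether synonymous and untranslated-region variants count as pathogenic, which item (4) does not say.

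Two lesser faults lie in the same list. Item (2) repeats the affected-relative threshold of 6.1 but adds a condition on patients and generations that is garbled and absent from 6.1. Item (6) names only normal cognition and dementia, although item (10) defines MCI and 4.1 recruits both pre-MCI and MCI.

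**What to change.** Reconcile 6.2(4) with 6.1 and aim 3.1 in one of two ways:

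- **(a)** Take it out of the entry conditions and make it a classification rule: an APP/PSEN1/PSEN2 pathogenic mutation found in the pedigree places it in the ADAD subcohort; none found places it in the un-FAD subcohort.
- **(b)** Keep it as a criterion, under the heading: ADAD cohort only.

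In the same amendment, state one affected-relative condition in both 6.1 and 6.2(2), with the generation clause rewritten so that a site can apply it, and name pre-MCI and MCI in 6.2(6).

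The cost is protocol wording, with the ethics committee approval that 11.2 requires for any modification. The change to item (4) brings eligibility into line with the population already described. Settling item (2) could alter who qualifies, because 6.1 has no generation condition, so the sponsor should choose that wording deliberately. No new procedures, data or analyses follow.

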6.3 Exclusion criteria

(1) Dementia caused by other factors such as depression, other psychiatric illnesses, thyroid dysfunction, encephalitis, multiple sclerosis, brain trauma, brain tumor, syphilis, acquired immunodeficiency syndrome (AIDS), Creutzfeldt-Jakob disease and other types of dementias such as vascular dementia (VaD), frontotemporal dementia (FTD[36]), dementia with Lewy bodies (DLB[37]), and Parkinson's dementia (PDD);

(2) MRI and laboratory tests do not support or rule out a diagnosis of AD;

(3) Severe circulatory, respiratory, urinary, digestive, hematopoietic diseases (such as unstable

angina, uncontrollable asthma, active gastric bleeding) and cancer;

(4) Participant has severe psychiatric illness or severe dementia that would interfere in completing initial and follow-up clinical assessments;

(5) Participant has a history of alcoholism or drug abuse;

(6) Pregnant or lactating women;

(7) No reliable informant;

(8) Lumbar puncture exclusion criteria: coagulation disorders or platelet counts $< 100,000$ cells/ μL , lumbar surgery within the last 6 months prior to lumbar puncture that interferes with anatomy of the inter-vertebral spaces, History of chronic or repeated CSF leakage following previous LP(s);

(9) MRI Exclusion Criteria: electronic and magnetic metal implants such as pacemakers, artificial heart valve, metal prosthesis, metal joint, etc.; metallic foreign body in the eye; aneurysm clips in the brain.

6.4 Study discontinuation

The primary reasons for study discontinuation are:

(1) Protocol violation. The participant fails to meet inclusion criteria, or meets exclusion criteria.

(2) Participant is unwilling or unable to participate.

(3) Consent is withdrawn.

(4) The study is terminated by the project director or the CFAN administration center.

(5) Safety Risk. Any participant who develops safety risk at any time during the visit.

(6) Death.

(7) Others.

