6.5 Baseline visit

The baseline study visit includes the following items:

(1) Explain study contents and procedures to participant and sign the informed consent form.

(2) Urine pregnancy test (for women of childbearing potential).

(3) Check inclusion/exclusion criteria.

(4) Blood, urine and saliva samples collection (biomarkers).

(5) Genetic testing to examine risk gene *APOE* and known pathogenic genes *PSEN1*, *PSEN2*, and *APP* for all participants.

(6) Collecting participant and informant demographics.

(7) Collecting family history and draw family tree.

(8) Previous medical, medication history and life style.

(9) Physical exam and vital signs.

(10) Neurological Exam.

(11) Neuropsychological test: Mini-Mental State Examination (MMSE), Montreal Cognitive Assessment (MoCA), Neuropsychiatric Inventory Questionnaire (NPI-Q), Hamilton Anxiety Scale (HAMA), Hamilton Depression Scale (HAMD), Modified Hachinski Ischemic Scale (m-HIS), the world health organization university of California-Los Angeles auditory verbal learning Test (WHO-UCLA AVLT), Rey-Osterrieth Complex Figure Test (ROCFT), Digit Span Forward (DSF), Digit Span Backward (DSB), Verbal Fluency Test (VFT), Trail Making Test (TMT) A/B, Boston Naming Test (BNT), Clinical Dementia Rating (CDR), Activities of Daily Living (ADL).

(12) MRI includes the following: conventional scan T1 weighted image (T1WI), T2 weighted image (T2WI), T2 FLAIR and hippocampal scan coronary T1-FLAIR sequence.

(13) ¹⁸F-FDG PET.

(14) ¹¹C-PIB PET.

(15) Carotid ultrasound.

(16) Lumbar puncture to examine cerebrospinal fluid (after MRI exams) and follow-up phone call (if participate in LP)

(17) After informed consent, non-pharmaceutical interventions are carried out on non-onset gene mutation carriers in the family, including lifestyle changes, increased physical exercise and cognitive training, and nootropic drugs.

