6.6 Follow-up in-person visits

The follow-up interval will be determined by the age of the individual in relation to the parent's Average Age of Onset (AAO) or pedigree mean AAO. The affected parent's AAO or pedigree mean AAO is used as the index for the frequency of assessments as follows in **Table 1**. In the years between in-person visits, telephone follow-up will be carried out every six months to inquire about cognitive change. If cognitive changes are reported by the participant and/or the informant during the telephone follow-up, the follow-up plan will be advanced and the participant will have a in-person clinical assessment.

Follow-up study visit includes the following items:

- (1) Urine pregnancy test (for women of childbearing potential)
- (2) Blood, urine and saliva samples collection (biomarkers)
- (3) Family history update
- (4) Participant and informant demographics
- (5) Medical and concurrent medications history
- (6) Physical exam and vital signs
- (7) Neurological exam

(8) Neuropsychological test: Mini-Mental State Examination (MMSE), Montreal Cognitive Assessment (MoCA), Neuropsychiatric Inventory Questionnaire (NPI-Q), Hamilton Anxiety Scale (HAMA), Hamilton Depression Scale (HAMD), Modified Hachinski Ischemic Scale (m-HIS), the world health organization university of California-Los Angeles auditory verbal learning Test (WHO-UCLA AVLT), Rey-Osterrieth Complex Figure Test (ROCFT), Digit Span Forward (DSF), Digit Span Backward (DSB), Verbal Fluency Test (VFT), Trail Making Test (TMT) A/B, Boston Naming Test (BNT), Clinical Dementia Rating (CDR), Activities of Daily Living (ADL).

(9) MRI includes the following: conventional scan T1 weighted image (T1WI), T2 weighted image (T2WI), T2 FLAIR and hippocampal scan coronary T1-FLAIR sequence.

(10) ¹⁸F-FDG PET.

(11) ¹¹C-PIB PET.

(12) Carotid ultrasound.

(13) Lumbar puncture to examine cerebrospinal fluid.

Table 1 Follow-up visit plan and frequency

Index: Individual compared with parent's AAO or pedigree mean AAO	In-person assessment interval
> 10y younger	every 5 years
10y – >3y younger	every 3 years
3y – 0y younger	annual
0y – <3y older	annual
≥ 3y older	once, at 5 years older than parent's AAO
*Documented cognitive decline on telephone follow-up, confirmed by an in-person clinical assessment	every six months

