Telephone follow-up will occur as indicated in the schedule of events in order to maintain contact with the family, inquire about cognitive change, and update information about adverse effect.

7. Assessments

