7.4.3 Carotid ultrasound

Carotid ultrasound can clearly demonstrate the vascular intima-media thickness, the location and size of plaque, the degree of vascular stenosis, and analyze hemodynamics. It plays a key role in the assessment and diagnosis of vascular-related diseases caused by atherosclerosis. Carotid ultrasound examination should be performed within 1 month before or after neuropsychological examination (with no new vascular disease event). An experienced ultrasound physician is required to perform the operation according to "Guidelines for Carotid Ultrasound Examination". Longitudinal and transverse

section scanning are performed from frontal and lateral directions. Observe and record the peak systolic velocity (PSV), end diastolic velocity (EDV), intima-media thickness (IMT) and plaque (diameter, number, acoustic properties) of internal carotid artery, common carotid artery and carotid bifurcation.

8. Statistical analysis

Periodic review of the accumulating data will be made to safeguard the statistical quality of the data and to ascertain whether they conform to the expectations of the original statistical design. At the same time, the statistician will perform statistical quality control of FAD data, focusing on outlier and missing data detection and comparison among sites. Then, the statistician will participate in statistical data analyses, consultations and reporting using R software and other statistical software, such as SAS and SPSS for specialized statistical analyses. The sample size is calculated using the paired sample t test, and the statistical test level is set to 0.05.

The normality and homogeneity of variance tests were performed on continuous variables. Data that passed these two tests were presented as mean \pm standard deviation, then underwent t-testing for comparisons between two groups and one-way analysis of variance (ANOVA) testing for comparisons among three or more groups. After ANOVA analysis, a Dunnett's multiple comparison test was used for post hoc testing. Data that did not pass the normality test were presented as quartiles, and underwent nonparametric testing, using the Kruskal-Wallis test and Dunn's multiple comparison test for comparisons among three or more groups. The significance of differences was assessed by the χ^2 test for categorical variables. The correlation between variables were calculated using Pearson or Spearman method.

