10.3 Subject's compliance

(1) Signing informed consent forms;

(2) The investigators should conscientiously implement the informed consent so that the subjects can fully understand the trial requirements and cooperate with the trial. The sponsor provides trial drugs free of charge and cover the laboratory examination costs.

11. Ethics

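### Safety reason in 6.4(5) is tied to the visit and ends study participation, while adverse effects are collected between visits with no stated consequence and treated carriers may be lost to follow-up

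*Protocol*

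**What the plan says.** - **Intervention.** Section 6.5(17) says that, after consent, "non-pharmaceutical interventions are carried out on non-onset gene mutation carriers in the family". The list of components has drugs in it although its label says otherwise; it is worded as "including lifestyle changes, increased physical exercise and cognitive training, and nootropic drugs". Section 10.3 adds that "The sponsor provides trial drugs free of charge and cover the laboratory examination costs".
- **Safety reason.** Section 6.4 opens with "The primary reasons for study discontinuation are" and gives as item (5) "Safety Risk. Any participant who develops safety risk at any time during the visit". No other item in the list concerns safety. Items (2), (3) and (7) cover unwillingness or inability to take part, withdrawn consent, and other reasons.
- **Contact schedule.** Table 1 in Section 6.6 sets in-person intervals of 5 years, 3 years or 1 year according to distance from the expected age at onset, and six months after confirmed decline. Telephone calls are six-monthly in the years between in-person visits.
- **What the calls do.** "If cognitive changes are reported by the participant and/or the informant during the telephone follow-up, the follow-up plan will be advanced". The calls are also there to "inquire about cognitive change, and update information about adverse effect". No step is attached to a reported adverse effect.
- **Other safety provision.** Section 12.2 makes qualified or trained researchers responsible for taking safety consultations at any time.
- **Data review.** Section 8 says "Periodic review of the accumulating data will be made to safeguard the statistical quality of the data" and goes on to outliers, missing data and comparison among sites. Adverse effects are not mentioned.
- **Use of the data.** Sections 3.6 and 4.6 plan to analyse how nootropic drugs, exercise, cognitive training and lifestyle affect progression in patients and asymptomatic carriers.

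**The concern.** Two features of 6.4(5) fit poorly with a study that treats some of its participants.

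The first is scope. Exposure to a drug or an exercise programme continues between visits, but the safety reason is worded around the visit. The contact that does occur between visits asks about adverse effects, and the protocol does not say what follows when one is reported.

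The second is the level at which the rule acts. It ends participation in the study. Nothing in the protocol separates stopping an intervention from leaving the cohort, and nothing says that observation continues after a safety-related stop. A carrier who stops for safety reasons would then contribute no later cognition, imaging or biomarker data, and the outcome of the harm itself would go unobserved.

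The statistical stake is missing data related to the intervention, in the group whose progression under intervention the study wants to describe.

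**Working it through.** The protocol gives no figure to reproduce, so the check sets the sections side by side. The only arithmetic is a count of contacts.

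**1. When does the safety reason apply?** Section 6.6 speaks of telephone follow-up taking place between in-person visits and never calls the telephone contacts visits. Read literally, 6.4(5) does not reach them. Inputs are the Table 1 intervals and the six-monthly call rule.

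| Table 1 band | Calls in years without a visit | Calls / all contacts per cycle | If a call falls at every six-month point |
|---|---|---|---|
| 5-year interval | 4 × 2 = 8 | 8/(8+1) = 89% | 9/(9+1) = 90% |
| 3-year interval | 2 × 2 = 4 | 4/(4+1) = 80% | 5/(5+1) = 83% |
| Annual | 0 × 2 = 0 | 0/(0+1) = 0% | 1/(1+1) = 50% |

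These are shares of scheduled contacts, not of adverse effects, and they matter only if the visit wording is taken literally. They show that the wording matters most for carriers more than 3 years younger than the expected age at onset, and least in the annual bands.

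**2. What follows a report by telephone?**

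| Reported by telephone | Recorded? | Stated next step |
|---|---|---|
| Cognitive change | Yes (6.6) | In-person assessment is brought forward (6.6) |
| Adverse effect | Yes (6.6) | None stated |

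**3. What does a safety-related stop do?** Item (5) stands in a list of reasons for study discontinuation. If the visit wording is read generously as any time in follow-up, step 1 falls away but this step does not: the item still ends participation. Using item (2), (3) or (7) for a participant harmed between visits has the same result.

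**4. Whom does the loss affect?** Section 6.5(17) names only non-onset carriers for intervention. Loss caused by an intervention would therefore arise among carriers and have no counterpart among noncarriers. Two analyses depend on carrier follow-up: the intervention effects in 3.6 and 4.6, and the longitudinal model in Section 8, which relates each marker to mutation status and estimated years from onset.

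**5. How large, and in which direction?** The protocol gives no adverse-effect rate, no number of treated carriers and no expected rate of safety-related stops. Neither the size nor the direction of any bias can be derived.

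**The case against.** The strongest reply is that the protocol is not silent on safety between visits. Calls update adverse-effect information, Section 12.2 provides a contact for safety matters at any time, and each follow-up visit repeats medication history, physical examination and vital signs. The English is uneven elsewhere, for instance in inclusion criterion (2), so the visit wording may loosely mean follow-up. The list in 6.4 gives primary reasons, not all reasons. Standard operating procedures and an investigator's brochure are mentioned in Section 10 and may say more.

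Much of this stands, and it rules out several stronger readings that a reader might infer:

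- **That harm between visits triggers nothing or goes unseen.** It is asked about and there is someone to contact. What is missing is a stated consequence.
- **That harmed carriers are removed from the data.** Nothing says that data already collected are dropped. Only later follow-up is at issue.
- **That treated carriers would appear to tolerate the interventions better than they did.** Aims 3.6 and 4.6 concern progression, and a recorded safety discontinuation would itself be evidence of poor tolerance. No direction of bias is shown.
- **That nobody reviews adverse effects across the 68 centres.** This argues from silence. Section 9.3 has a quality control committee check all data, though not expressly for safety.
- **That 89% or 80% of harm would be missed.** The figures cover the two longest bands only and count contacts.

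The reply does not answer the second feature. However the visit wording is read, a safety stop ends participation, and no section says that observation continues.

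**Conclusion.** The point holds in a limited form. Section 6.4(5) ties its safety reason to the visit and applies it to the whole study, while 6.5(17) starts interventions including drugs in symptom-free carriers and 6.6 collects adverse effects between visits up to 5 years apart without saying what follows. As written, a safety-related stop ends later follow-up. Such loss would fall on carriers and be related to the intervention whose effect on progression is to be analysed.

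The conclusion on lost follow-up rests on reading study discontinuation as the end of later assessments, which is its ordinary meaning and which the protocol nowhere qualifies. The conclusion on scope rests in addition on a literal reading of the visit wording and is weaker for that reason. The size and direction of any bias remain unknown. The inconsistency should be corrected because the remedy is cheap and follow-up once ended is hard to recover. It does not invalidate the cohort.

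**What to change.** 1. Reconcile 6.4(5), 6.5(17), Table 1 and the telephone text in 6.6, so that they agree on when the safety reason applies and on what follows a reported adverse effect. Any clinical rule, including which events matter and what is done about them, is for the sponsor's clinicians to set; none is proposed here.
2. State in 6.4 that a participant whose intervention is stopped remains in observational data collection unless consent is withdrawn or further assessment is judged unsafe. Record the stop of an intervention separately from the end of study participation, with date and reason for each.
3. Add a table of adverse effects by intervention received to the periodic review in Section 8.

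The cost is a few sentences of protocol wording and one extra table in a review already planned. Sites would also continue data collection on participants who would otherwise have left.
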